7.2.3. Clinical Response Categories

Investigator assessment of response should include physical examination, radiographic imaging, and evaluation of blood and marrow (if applicable). For response assessments not requiring a CT scan, the Investigator should evaluate response based on available clinical data, including physical examinations and laboratory results. Definition of response for CR, CRi, nPR, PR, PRL and disease progression will be evaluated by the criteria listed in Table 15. Group A criteria define the tumor load and Group B criteria define the function of the hematopoietic system. Response must be confirmed by CT when available, and must last at least 2 months without transfusional support or growth factor product to be considered a confirmed response.

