7.2.3.1. Complete Response (CR)

All of the following are required for a CR:

- No significant lymphadenopathy (>1.5cm) palpable on examination or by CT
- No hepatosplenomegaly on examination or by CT
- No constitutional symptoms (ie, no fever >38°C for ≥2 weeks, no ongoing unintentional ≥10% body weight loss, no night sweats for >1 month without other evidence of infection, no fatigue interfering with work or usual activities) attributable to CLL.
- Neutrophils >1500/μL, platelets >100,000/μL, and Hgb >11g/dL without recent growth factor or transfusions
- ALC <4,000/μL

Marrow aspirate and biopsy must be performed after all other criteria meet the definition of CR. To define a CR, the marrow sample must be at least normocellular for age, with less than 30% of nucleated cells being lymphocytes. B-lymphoid nodules should be absent.

In addition, in subjects with a CR, MRD should be performed on both peripheral blood and bone marrow aspirate to evaluate MRD status.

Table 15. Criteria for Clinical Response Categories

Parameter	CR	PR	PD
Group A			
Lymphadenopathy ^a	None; ≤1.5cm	Decrease ≥50%	increase ≥50%
Hepatomegaly	None	Decrease ≥50%	increase ≥50% or new hepatomegaly
Splenomegaly	None	Decrease ≥50%	increase ≥50% or new splenomegaly
Blood lymphocytes	<4000/μL	Decrease ≥50% from baseline	increase ≥50% over baseline ^c
Marrow ^b	Normocellular, <30% lymphocytes, no B lymphoid nodules. Hypocellular defines CRi ^d in a patient with cytopenias		
Group B			
Platelet count	>100,000/μL	>100,000/μL or increase ≥50% over baseline	Decrease of ≥50% from baseline secondary to CLL
Hemoglobin	>11 g/dL	>11 g/dL or increase ≥50% over baseline	Decrease of >2g/dL from baseline secondary to CLL
Neutrophils	>1500/μL	>1500/μL or increase ≥50% over baseline	N/A

- Sum of the products of multiple lymph nodes (as evaluated by CT scans) or the longest diameter of one target lymph node
- This parameter is not relevant for the PD category unless confirming cytopenic progression.
- Subjects with treatment-related lymphocytosis should remain on study treatment in the absence of other criteria for progressive disease (see [Section 7.2.1.2](#)).
- Hypocellular marrow is a CRi when peripheral blood cytopenias not meeting Group B criteria are present. CRi requires at least one abnormal Group B criteria.

Note: Group A defines the tumor load and Group B defines the function of the hematopoietic system

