CR: all of the criteria need to be met and subjects have to lack disease related constitutional symptoms.

Bone marrow and aspirate is required to confirm CR.

PR: At least two of the Group A parameters must be met; with two exceptions: 1) subjects who only have abnormal lymph nodes at baseline, or 2) subjects who have only abnormal lymph node and abnormal lymphocyte count (ALC) at baseline. For these two exceptions, subjects will only need to meet the lymph node response criteria.

In addition to the Group A criteria, all subjects must also have a response in at least one of the Group B criteria.

SD: the absence of PD and the failure to achieve a response.

PD: at least 1 of the above criteria from Group A or B are met or development of transformation to a more aggressive histology

Cross reference: [Hallek 2008](#), [Hallek et al. June 2012 e-letter](#), [Hallek 2013](#)

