7.2.3.4. Partial Response (PR)

At least two of the following parameters must be met; with two exceptions: 1) subjects who only have abnormal lymph nodes at baseline, or 2) subjects who have only abnormal lymph node and abnormal lymphocyte count (ALC) at baseline. For these two exceptions, subjects will only need to meet the lymph node response criteria.

- $\geq 50\%$ decrease in the sum products of up to 6 lymph nodes, a $\geq 50\%$ decrease in the longest diameter of the single lymph node, or normalization of lymphadenopathy when compared to baseline.
 - With no new enlarged lymph nodes by physical examination or CT AND no increase in any lymph node by CT. Note: In a small lymph node < 2 cm, an increase of less than 25% is not considered to be significant.
- When abnormal, a $\geq 50\%$ decrease in the enlargement of the spleen and/or liver from baseline or normalization by CT
- If abnormal a $\geq 50\%$ drop in lymphocyte count from baseline or $\leq 4000/\mu\text{L}$

In addition to the criteria above, the subject must also have a response in at least one of the following evaluable criteria independent of growth factor support or transfusion.

- Neutrophils $> 1500/\mu\text{L}$ or $\geq 50\%$ improvement over baseline
- Platelets $> 100,000/\mu\text{L}$ or $\geq 50\%$ improvement over baseline
- Hgb > 11 g/dL or $\geq 50\%$ improvement over baseline

* Note: For criterion to be considered in response evaluation, it must have been evaluable at baseline

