7.2.3.5. PR with Lymphocytosis (PRL)

Subjects achieve all PR criteria with the exception of lymphocyte criteria.

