Complete response rate (CRR)	The proportion of subjects achieving a best overall response of CR or CRi on or prior to initiation of subsequent antineoplastic therapy or, if applicable, reintroduction of study treatment, whichever occurs earlier.	
Primary The point estimate of CRR per investigator assessment and the corresponding 95% CI based on normal approximation to the binomial distribution will be provided. In FD cohort non-del17p population, p value for testing <math>CRR \leq 37\%</math> vs <math>CRR > 37\%</math> using asymptotic test for the binomial proportion will be calculated.
 
Sensitivity CRR per IRC assessment.
 
Supportive 1. Duration of complete response (DOCR defined as the interval between the date of initial CR or CRi until disease progression or death from any cause, whichever occurs first.) for subjects who achieved CR or CRi. 2. Durable CRR (defined as proportion of subjects with DOCR <math>\geq</math> 336 days (12 cycles))
 
Subgroup (defined in table 1) The point estimate of CRR per investigator assessment and its 95% CI by normal approximation to the binomial distribution for each subgroup.

Secondary Endpoints for MRD and FD Cohorts		
Overall response rate (ORR)	The proportion of subjects achieving a best overall response of CR, CRi, nPR, or PR on or prior to initiation of subsequent antineoplastic therapy or, if applicable, reintroduction of study treatment, whichever occurs earlier.	
Primary The point estimate of ORR per investigator assessment and the corresponding 95% CI based on normal approximation to the binomial distribution will be provided.
 
Sensitivity ORR per IRC assessment.

Duration of response (DOR)	Duration of response will be calculated for the subjects achieving a response (CR, CRi, nPR, PR) per investigator assessment and is defined as time from the date of initial response including PR with lymphocytosis to the date of disease progression or the date of death from any cause, whichever occurs first. For subjects without documented PD or death, DOR was censored at the date of last adequate disease assessment.	
Primary Kaplan-Meier estimates of median DOR time per investigator assessment and landmark estimates with 2-sided 95% CIs.
 
Sensitivity DOR per IRC assessment

Endpoint	Definition	Analysis Method

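### Table 15 and section 7.2.3.4 of the protocol state different partial-response rules, and PR overlaps PRL, which can change who counts in ORR and DOR

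*Protocol*

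**What the plan says.** Protocol section 7.2.3 names the rule: "Definition of response for CR, CRi, nPR, PR, PRL and disease progression will be evaluated by the criteria listed in Table 15". The notes to Table 15 then set the count: "PR: At least two of the Group A parameters must be met; with two exceptions". Section 7.2.3.4 uses the same count and the same two exceptions (only nodes, or only nodes and ALC, abnormal at baseline; the node response is then enough), but attaches them to different parameters.

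| Element | Table 15, PR column and notes | Section 7.2.3.4 |
|---|---|---|
| Nodes | fall of at least 50%, measured as "Sum of the products of multiple lymph nodes (as evaluated by CT scans) or the longest diameter of one target lymph node" | fall of at least 50% in the sum of products; or a 50% "decrease in the longest diameter of the single lymph node, or normalization of lymphadenopathy when compared to baseline" |
| Liver, spleen | two rows, each a fall of at least 50% | one item: a 50% "decrease in the enlargement of the spleen and/or liver from baseline or normalization by CT" |
| ALC | "Decrease ≥50% from baseline" | same fall, or 4000/µL or less |
| New or growing nodes | no condition for PR | none allowed, apart from a small-node tolerance |
| Group B | one of platelets, hemoglobin, neutrophils; no baseline condition stated | one of the three, and only if evaluable at baseline |

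Table 14 makes a blood count evaluable only if it is low at baseline (platelets 100,000/µL or less, ANC 1500/µL or less, hemoglobin 11.0 g/dL or less).

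PRL is defined in section 7.2.3.5: "Subjects achieve all PR criteria with the exception of lymphocyte criteria". Table 15 has no PRL column.

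Protocol section 10.4.3 counts PRL in ORR. SAP Table 2 does not: "The proportion of subjects achieving a best overall response of CR, CRi, nPR, or PR on or prior to initiation of subsequent antineoplastic therapy". In both documents DOR is computed for CR, CRi, nPR and PR, with the clock starting at first response, PRL included.

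**The concern.** Two passages of the same protocol section define PR and do not agree, in either direction. A subject can therefore be a responder under one and not under the other. PRL is carved out of PR by a criterion that PR does not require, so the two categories share subjects. ORR and DOR are secondary endpoints in both cohorts, and the SAP adds IRC versions of each as sensitivity analyses. If the rule is left open, part of what these endpoints report reflects which paragraph was applied.

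**Working it through.** No figure in the plan rests on the PR definition: the sample sizes use the 1-year disease-free rate and the CR rate. The check is to apply both rules literally to constructed subjects.

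**1. Normalization.** A target node must exceed 1.5 cm at baseline, and the CR limit is 1.5 cm or less. A single node of baseline size b that ends at 1.5 cm has fallen by 1 - 1.5/b, which is below 50% for any b below 3.0 cm.

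Example: only nodes and ALC abnormal in Group A at baseline, one target node.
- Node 2.4 to 1.4 cm: 1 - 1.4/2.4 = 41.7%.
- ALC 7.0 to 3.8 x10^9/L: 1 - 3.8/7.0 = 45.7%, and now below 4.0.
- Hemoglobin low at baseline and recovered. Marrow still has 30% or more lymphocytes, so the subject is neither CR nor nPR.

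Table 15: the node has not halved, so SD. Section 7.2.3.4: the node is normal, so PR.

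With several nodes the sum of products applies. If both diameters shrink in proportion, the product halves at 0.707 of the baseline diameter, so the gap remains only below 1.5/0.707 = 2.1 cm. The same 2.4 to 1.4 cm change is then 1 - (1.4/2.4)^2 = 66%, which passes.

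**2. Organ count.** Nodes -30%, liver and spleen each -60%, ALC normal at baseline, low hemoglobin recovered. Table 15: two parameters, PR. Section 7.2.3.4: one parameter, not PR.

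**3. Node growth.** Sum of products -60%, one node +30% (below the 50% limit for PD), no organ enlargement, cytopenia recovered. Table 15: PR. Section 7.2.3.4: not PR.

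**4. Group B.** Nodes -60%, nothing else abnormal, no baseline cytopenia. Table 15 read alone: platelets above 100,000/µL suffice, PR. Section 7.2.3.4: no blood count was evaluable, so PR is out of reach. If Table 14 is applied to Table 15 as well, the passages agree here, but such a subject can reach PR under neither. Section 4.1 sets only lower limits for counts, so these subjects can enroll.

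**5. PR and PRL.** Nodes and spleen each -60%, cytopenia recovered, ALC still raised as treatment-related lymphocytosis. Two parameters are met without ALC, so this is PR under either rule. It also meets every PR criterion except lymphocytes, so it is PRL. The exception for nodes plus ALC gives the same overlap.

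**How often, logically.** I crossed 3 node, 4 spleen, 4 liver, 4 ALC, 2 node-growth and 4 cytopenia states and dropped the combinations pairing normalized nodes with growth: 1,536 - 256 = 1,280. Both rules give PR in 85, neither in 847, only Table 15 in 245, only 7.2.3.4 in 103. They disagree in 245 + 103 = 348.

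Table 15 meets Group B in three of the four cytopenia states, so (85 + 245)/3 = 110 of 320 tumor-load combinations pass it. Section 7.2.3.4 meets Group B in one state, where 85 + 103 = 188 of 320 pass. In that shared state (110 - 85) + 103 = 128 disagree; the other 348 - 128 = 220 come from the Group B wording alone.

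**What each split changes.**

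| Split | Protocol ORR | SAP ORR | DOR set | DOR start |
|---|---|---|---|---|
| PR or SD | yes | yes | yes | possibly |
| PR or PRL | no | yes | yes | no |

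**Size per subject.** 1/125 = 0.8 points in the Fixed Duration cohort; 1/150 = 0.67 points in the MRD cohort. If 2 to 5 subjects were affected (an assumption), ORR would move 1.6 to 4.0 points or 1.3 to 3.3 points.

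**The case against.** The best reply is that the protocol does name a rule and little depends on it. Section 7.2.3 points to Table 15. SAP section 1.1 refers to the IWCLL guideline with later clarifications, and its reference list includes a 2013 clarification on partial response. Testing is confined to the primary endpoints (SAP section 1.6), and neither primary endpoint, nor PFS, OS or the sample sizes, uses PR. The normalization gap is narrow when several nodes are followed. Lymphocytosis resolves at a median of 14 weeks (protocol section 1.2.4.8), so an early PRL label will often be superseded.

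The limits on size stand. The claim that the rule is settled does not. Section 7.2.3.4 gives a full rule of its own and is not made subordinate to Table 15. Table 15 cannot define PRL. Applied alone, it lets a node meet the CR limit and fail the PR limit. The 2013 clarification is not in the documents, so whether it resolves the conflict cannot be judged here.

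A reader might infer more than the documents support:
- That no passage governs. One is named; a second contradicts it.
- That about a quarter of subjects are affected (348 of 1,280). These are logical combinations, not frequencies.
- That PR versus PRL moves ORR everywhere. It moves only the SAP's ORR.
- That one subject can readily be PR, PRL and SD. This needs raised ALC, no baseline cytopenia, and Table 15 read without Table 14.
- That investigator and IRC reads will diverge because of the rule. The IRC charter is not available, so this is only a possibility.

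**Conclusion.** The two PR rules conflict on thresholds, on the liver and spleen count, on node growth and, unless Table 14 is read into Table 15, on Group B. PRL overlaps PR. Subjects whose best response is CR, CRi or nPR stay responders either way, so responder status changes only for those whose best response is PR or PRL under at least one rule.

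The consequence is confined to ORR and DOR, both reported descriptively. The per-subject shift rests on the planned cohort sizes of 125 and 150. The total cannot be derived, because the documents do not say how many subjects would fall in the gap. The PR/PRL overlap matters mainly because the two ORR definitions differ, and SAP section 6 does not list that difference as a change from the protocol. This is worth correcting before ORR and DOR are derived, but it does not threaten either primary analysis.

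**What to change.** Put one PR rule in both places:
- Add normalization as an alternative for nodes, liver and spleen in Table 15, and 4000/µL or less as an alternative for ALC.
- Count liver and spleen the same way in both passages.
- State the bar on new or growing nodes identically.
- State the Group B baseline condition identically, worded so that subjects without baseline cytopenia are not shut out of PR by wording alone.

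Then say in section 7.2.3.5 how PR and PRL are separated, consistently with the exception for subjects with only nodes and ALC abnormal. Simply labelling every unmet lymphocyte criterion as PRL would cancel that exception, which both passages state, and would remove those subjects from the SAP's ORR and from the DOR set.

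Reconcile the ORR definitions in protocol section 10.4.3 and SAP Table 2. If PRL counts in both, the PR/PRL label no longer affects ORR and matters only for the DOR set. Use the same text for investigator and IRC reads.

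The cost is wording in the protocol, SAP and IRC charter. A few PR, PRL or SD labels may need to be derived again; no new data are needed.

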7.2.3.2. Complete Response with an Incomplete Marrow Recovery (CRi)

Complete response with an incomplete marrow recovery (CRi) is defined as a CR with an incomplete recovery of the subject's bone marrow, manifested by persistent cytopenias. Subjects who have a CRi fulfill all criteria for a CR, but continue to have persistent anemia, thrombocytopenia, or neutropenia. These cytopenias are due to drug toxicity in the bone marrow and are not due to any evidence of CLL. If the marrow is hypocellular, a repeat determination should be performed after 4 weeks, or when peripheral blood counts have recovered. However, this time interval should not exceed 6 months.

7.2.3.3. Nodular Partial Response (nPR)

Nodular partial response (nPR) is a response where subjects meet criteria for a CR, but the bone marrow biopsy shows that there are still B-lymphoid nodules, which may represent a clonal infiltrate. These nodules or aggregates are residual disease and therefore the subject is termed an nPR. Immunohistochemistry may be performed to define whether the nodules or aggregates comprise primarily T cells, B cells other than CLL cells, or CLL cells. If nodules or aggregates are not composed of CLL cells, a CR can be documented provided all other criteria are met.

7.2.3.4. Partial Response (PR)

At least two of the following parameters must be met; with two exceptions: 1) subjects who only have abnormal lymph nodes at baseline, or 2) subjects who have only abnormal lymph node and abnormal lymphocyte count (ALC) at baseline. For these two exceptions, subjects will only need to meet the lymph node response criteria.

- $\geq 50\%$ decrease in the sum products of up to 6 lymph nodes, a $\geq 50\%$ decrease in the longest diameter of the single lymph node, or normalization of lymphadenopathy when compared to baseline.
 - With no new enlarged lymph nodes by physical examination or CT AND no increase in any lymph node by CT. Note: In a small lymph node < 2 cm, an increase of less than 25% is not considered to be significant.
- When abnormal, a $\geq 50\%$ decrease in the enlargement of the spleen and/or liver from baseline or normalization by CT
- If abnormal a $\geq 50\%$ drop in lymphocyte count from baseline or $\leq 4000/\mu\text{L}$

In addition to the criteria above, the subject must also have a response in at least one of the following evaluable criteria independent of growth factor support or transfusion.

- Neutrophils $> 1500/\mu\text{L}$ or $\geq 50\%$ improvement over baseline
- Platelets $> 100,000/\mu\text{L}$ or $\geq 50\%$ improvement over baseline
- Hgb > 11 g/dL or $\geq 50\%$ improvement over baseline

* Note: For criterion to be considered in response evaluation, it must have been evaluable at baseline

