3.3. Study Schema; Fixed Duration Cohort

¹ Administer 12 cycles of ibrutinib + venetoclax unless discontinue for PD or toxicity. Subjects who discontinue treatment for reasons other than confirmed PD should continue participating in ongoing response follow-up visits until confirmed PD

² Refer to [Sections 3.1.3](#) and [5.3.3](#) for details regarding FD cohort Reintroduction

4. **SUBJECT SELECTION**

4.1. **Inclusion Criteria**

Prior to enrollment, each potential subject must satisfy all of the following inclusion criteria.

Disease Related

1. Diagnosis of CLL/SLL that meets IWCLL diagnostic criteria (Hallek 2008).
2. Active disease meeting at least 1 of the following IWCLL criteria (Hallek 2008) for requiring treatment:
 - Evidence of progressive marrow failure as manifested by the development of, or worsening of, anemia and/or thrombocytopenia
 - Massive, progressive, or symptomatic splenomegaly
 - Massive nodes or progressive or symptomatic lymphadenopathy
 - Progressive lymphocytosis
 - Constitutional symptoms
3. Measurable nodal disease by computed tomography (CT).

Laboratory

4. Adequate hematologic function independent of transfusion and growth factor support for at least 7 days (with the exception of pegylated G-CSF [pegfilgrastim] and darbopoeitin which require at least 14 days) prior to screening laboratory assessment defined as:
 - Absolute neutrophil count (ANC) >750 cells/ μL (750 cells/ mm^3 or $0.75 \times 10^9/\text{L}$)
 - Platelet count $>30,000/\mu\text{L}$ (30,000 cells/ mm^3 or $30 \times 10^9/\text{L}$)
 - Hemoglobin >8.0 g/dL
5. Adequate hepatic and renal function defined as:
 - Serum aspartate transaminase (AST) or alanine transaminase (ALT) $\leq 3.0 \times$ upper limit of normal (ULN)
 - Creatinine Clearance (CrCl) ≥ 60 mL/min (eg, as estimated by Cockcroft-Gault)
 - Bilirubin $\leq 1.5 \times$ ULN (unless bilirubin rise is due to Gilbert's syndrome or of non-hepatic origin)
6. Prothrombin time (PT)/International normal ratio (INR) $<1.5 \times$ (upper limit of normal) ULN and PTT (activated partial thromboplastin time [aPTT]) $<1.5 \times$ ULN (unless abnormalities are unrelated to coagulopathy or bleeding disorder).

Demographic

7. Men and women ≥ 18 and ≤ 70 years of age.
8. Eastern Cooperative Oncology Group (ECOG) performance status of 0-2.

Ethical/Other

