7.2.2. Guidelines for Clinical Disease Evaluation

Objective response will be categorized as CR, CR with incomplete bone marrow recovery (CRi), nodular partial response (nPR), partial response (PR), PR with lymphocytosis (PRL), stable disease (SD), or progressive disease (PD)—all based upon IWCLL criteria ([Hallek 2008](#), [Hallek 2012](#), [Hallek 2013](#), [Cheson 2012](#)). All responses must be maintained for at least 2 months to be considered confirmed. CRs must be confirmed by bone marrow biopsy/aspirate. Response assessments on treatment arms will occur independent of ongoing therapy. For purposes of this protocol, 2 months equals 2 cycles (56 days) with each cycle equaling 28 days.

Given the known mechanism of action of BCR-inhibiting agents, including ibrutinib, and the treatment-related lymphocytosis frequently observed during treatment with ibrutinib, isolated treatment-related lymphocytosis (in absence of other clinical, CT, or laboratory evidence of disease progression) will not be considered progressive disease. This approach is supported by

both the authors of the IWCLL 2008 and 2017 guidelines (Hallek 2012, Cheson 2012) and the NCCN.

The requirement for each parameter at baseline to be evaluable throughout the study is outlined in Table 14.

Table 14. Evaluable Parameter Requirements

Parameter	Requirements to be Evaluable for Response
Measurable Disease (required for all subjects)	Lymph Node >1.5cm
Splenomegaly	Enlarged spleen
Hepatomegaly	Enlarged liver
Absolute Lymphocyte Count (ALC)	≥4,000/μL
Platelets	≤100,000/μL
Absolute Neutrophil Count (ANC)	≤1500/μL
Hemoglobin	≤11.0 g/dL

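### The partial-response rule contradicts itself for subjects with no baseline cytopenia: Section 7.2.3.4 with Table 14 gives stable disease, Table 15 gives PR

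*Protocol*

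**What the plan says.** Four pieces of Protocol Section 7.2 govern PR.

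- **Section 7.2.3.4.** Beyond the tumour-load criteria, "the subject must also have a response in at least one of the following evaluable criteria independent of growth factor support or transfusion". The counts listed are neutrophils, platelets and haemoglobin. The note that closes the section reads: "For criterion to be considered in response evaluation, it must have been evaluable at baseline".
- **Section 7.2.2, Table 14.** The section says that "The requirement for each parameter at baseline to be evaluable throughout the study is outlined in Table 14". Under the column "Requirements to be Evaluable for Response", the limits are platelets at or below 100,000/µL, ANC at or below 1500/µL and haemoglobin at or below 11.0 g/dL. Only measurable nodal disease is marked as required for everyone.
- **Section 7.2.3 and Table 15.** Section 7.2.3 sends the classification of every response category to Table 15. There the PR column accepts platelets above 100,000/µL, haemoglobin above 11 g/dL or neutrophils above 1500/µL (or a rise of at least 50%), with no condition on the baseline value. The text under the table says "all subjects must also have a response in at least one of the Group B criteria".
- **The two exceptions.** For subjects whose only baseline abnormality is nodal, or nodal plus lymphocyte count: "For these two exceptions, subjects will only need to meet the lymph node response criteria".

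PRL is built on PR (Section 7.2.3.5): "Subjects achieve all PR criteria with the exception of lymphocyte criteria". On entry, inclusion criterion 2 (Section 4.1) is met by any one sign of active disease, for example "Massive nodes or progressive or symptomatic lymphadenopathy". The count limits in criterion 4 are floors.

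**The concern.** A subject can enrol with three normal blood counts. Under Section 7.2.3.4 and Table 14 that subject has no evaluable count, so a requirement to respond in at least one cannot be satisfied, however far the nodes and spleen shrink. Under Table 15 the requirement is satisfied as long as one count stays normal. One set of data thus yields stable disease or PR.

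ORR and DOR are secondary endpoints in both cohorts. SAP Table 2 reports each by investigator (primary) and by IRC (sensitivity), and tabulates MRD negativity by response group (CR/CRi; nPR/PR/PRL; others). If the strict text is used:

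- a best response of PR drops out of ORR and out of the DOR set. A best response of PRL drops out of ORR under Protocol Section 10.4.3 only, because the SAP's ORR does not count PRL;
- those subjects move to the residual group in the supportive MRD table;
- a subject who later reaches CR stays in DOR, but the response clock can start late, because DOR runs from the first response, including PRL.

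**Working it through.** The documents state no design figure for ORR or DOR, so there is nothing to reproduce. The check is one of logic, followed by an illustration of size.

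**1. One subject, two rules.** Baseline: enlarged nodes and spleen, ANC 4000/µL, platelets 200,000/µL, haemoglobin 13.5 g/dL. On treatment: nodes and spleen each down by at least 50%, a residual node that rules out CR, ANC 3800/µL, platelets 190,000/µL, haemoglobin 13.4 g/dL. Two Group A parameters are met. The enlarged spleen puts the subject outside both lymph-node exceptions.

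| Count | Low at baseline (Table 14)? | Usable under the 7.2.3.4 note? | Above the Table 15 PR threshold now? |
|---|---|---|---|
| ANC | 4000 ≤ 1500: no | no | 3800 > 1500: yes |
| Platelets | 200,000 ≤ 100,000: no | no | 190,000 > 100,000: yes |
| Haemoglobin | 13.5 ≤ 11.0: no | no | 13.4 > 11: yes |

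Section 7.2.3.4: no usable count and at least one needed, so neither PR nor PRL. By Section 7.2.3.6 the subject is stable disease. Table 15: three counts qualify and one is needed, so PR.

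**2. A comparison subject.** Platelets 80,000/µL rising to 150,000/µL: usable (80,000 ≤ 100,000) and met (150,000 > 100,000). Both rules agree. The conflict is confined to subjects with no count at or below its Table 14 limit.

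**3. Which categories are exposed.** The CR count criteria in Section 7.2.3.1 are absolute, and nPR (Section 7.2.3.3) is built on CR, so neither is blocked. CRi is not blocked either. Only PR and PRL are. On the strict text a subject with normal counts can be stable disease, nPR or CR, but never PR.

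**4. Size if the strict text is applied throughout.** ORR loss = (share responding short of CR/CRi) × (share with no baseline cytopenia), taking the two as independent.

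- Share short of CR/CRi: 100% − 75% = 25%, from the 20 treatment-naive, high-risk subjects in the single-centre study cited in Section 1.4.
- Share without baseline cytopenia: not in the documents; 20% to 60% assumed.

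| Assumed share without cytopenia | ORR loss | Of 125 (FD) | Of 150 (MRD) |
|---|---|---|---|
| 20% | 0.25 × 0.20 = 5 points | 6.25 | 7.5 |
| 40% | 0.25 × 0.40 = 10 points | 12.5 | 15 |
| 60% | 0.25 × 0.60 = 15 points | 18.75 | 22.5 |

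For the 25% input these are upper bounds, since part of that 25% may be nPR. The loss scales with that input. The relapsed/refractory study in Section 1.4 (47% CR/CRi, 100% response, so 53% short of CR/CRi) would give 10.6 to 31.8 points, but from a different population.

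**5. DOR start date.** In the FD cohort a response assessment falls just before Cycle 4 (Section 8.3.1.3.1) and a marrow is scheduled at Cycle 10 (Section 8.3.1.6). A subject who would be PR at the first and is shown to be CR at the second would lose about 6 cycles, 6 × 28 = 168 days, of DOR.

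**The case against.** The strongest reply is that Section 7.2.3 makes Table 15 the governing list, and Table 15 credits normal counts. On that footing nobody is lost. This stands in part. A reader might infer from Section 7.2.3.4 alone that subjects with normal counts can never be PR and that ORR and DOR will lose true responders. The documents do not support so firm a statement. They show two rules in conflict and do not say which one assessors use. But the reply does not remove the conflict, because the note in Section 7.2.3.4 is an explicit restriction in the section that defines PR.

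Second, a subject with nodal disease only may be covered by the written exception. Its wording can be read as waiving the blood-count requirement as well. Against that, it sits in the tumour-load paragraph, the count requirement follows as an addition, and the text under Table 15 applies that requirement to every subject. The point is unclear, so a node-only example does not prove the fault. A subject with an enlarged spleen or liver as well lies outside the exceptions on either reading.

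Third, SAP Section 1.1 ties both investigator and IRC assessment to the IWCLL criteria with later clarifications, and the IRC charter is a separate document. Assessors may already credit normal counts. A reader might infer that investigator and IRC results will diverge because they follow different paragraphs. That is possible but cannot be shown from these documents.

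Fourth, only the primary endpoints are formally tested (SAP Section 1.6), and neither uses PR. That is correct and limits the weight of the point.

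**Conclusion.** The contradiction is real. For a subject with no baseline cytopenia who falls outside the two lymph-node exceptions, Section 7.2.3.4 with Table 14 gives stable disease and Table 15 gives PR. For node-only and node-plus-lymphocyte subjects the text is ambiguous.

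The effect is limited to descriptive results: ORR, DOR (membership and start date) and the supportive MRD table. CRR in the FD cohort, 1-year DFS in the MRD cohort and every power figure stand.

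The loss cannot be fixed from the documents. At most about 5 to 15 points of ORR would go, if every assessor applied the strict text, 25% responded short of CR/CRi, 20% to 60% had no baseline cytopenia, and the two were independent. The 20% to 60% is an assumption. It would be tempting to treat every response short of CR/CRi as exposed, but nPR is not blocked, so the true figure would be smaller. If assessors follow Table 15, it is zero. The text should be corrected, but it does not threaten the trial's main conclusions.

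**What to change.** Reconcile Table 14, Table 15, the text beneath Table 15 and Section 7.2.3.4:

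1. Keep the baseline-evaluability note for the Group A criteria.
2. For Group B, add one sentence in line with Table 15: *A subject with one or more counts abnormal at baseline must show a response in at least one of them; a subject with none abnormal at baseline meets Group B if at least one count remains above its Table 15 PR threshold without growth factor or transfusion.*
3. State whether the node-only and node-plus-lymphocyte exceptions waive Group B.
4. Use the same text for investigator assessment, the IRC charter and the response programming.

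The cost is a short protocol clarification and matching lines in the charter and programming specification. It uses counts already collected and needs no new procedure. Tabulating the share of subjects with no count at or below its Table 14 limit at baseline would replace the assumed 20% to 60% with the actual figure.
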